5.2. Description and Handling of Study Drug

5.2.1. Formulation

5.2.1.1. Elvitegravir (EVG) 150 mg / cobicistat (COBI) 150 mg / emtricitabine (FTC) 200mg / tenofovir alafenamide (TAF) 10mg fixed-dose combination (E/C/F/TAF, Genvoya)

E/C/F/TAF tablets are capsule-shaped, film-coated green tablets and are debossed with "GSI" on one side of the tablet and "510" on the other side of the tablet. E/C/F/TAF tablets contain 150 mg of EVG, 150 mg of COBI, 200 mg of FTC, and 10 mg of TAF (as 11.2 mg of TAF fumarate).

The E/C/F/TAF tablet core contains silicon dioxide, croscarmellose sodium, hydroxypropyl cellulose, lactose monohydrate, magnesium stearate, microcrystalline cellulose, and sodium lauryl sulfate as inactive ingredients and are film-coated with indigo carmine aluminum lake, polyethylene glycol, polyvinyl alcohol, talc, titanium dioxide, and yellow iron oxide.

5.2.1.2. Bictegravir/Emtricitabine/Tenofovir alafenamide (B/F/TAF, Biktarvy) 50/200/25mg fixed-dose combination

B/F/TAF tablets are capsule-shaped, film-coated purplish-brown, debossed with "GSI" on one side of the tablet and "9883" on the other side of the tablet. Each tablet core contains 50 mg of bictegravir, 200 mg of emtricitabine, and 25 mg of TAF. In addition to the active ingredients, the

B/F/TAF tablets contain croscarmellose sodium, magnesium stearate, and microcrystalline cellulose. The tablet cores are film-coated with iron oxide red, iron oxide black, polyethylene glycol, polyvinyl alcohol, talc, and titanium dioxide.

5.2.2. Packaging and Labeling

- 5.2.2.1. Elvitegravir (EVG) 150 mg / cobicistat (COBI) 150 mg / emtricitabine (FTC) 200 mg / tenofovir alafenamide (TAF) 10 mg fixed-dose combination (E/C/F/TAF, Genvoya)

E/C/F/TAF tablets are packaged in white, high density polyethylene (HDPE) bottles. Each bottle contains 30 tablets, silica gel desiccant and polyester packaging material. Each bottle is enclosed with a white, continuous thread, child-resistant polypropylene screw cap with an induction-sealed, aluminum-faced liner.

Study drug to be distributed to centers in the US and other participating countries shall be labeled to meet applicable requirements of the United States Food and Drug Administration (FDA), EU Guideline to Good Manufacturing Practice – Annex 13 (Investigational Medicinal Products), and/or other local regulations.

- 5.2.2.2. Bictegravir/Emtricitabine/Tenofovir alafenamide (B/F/TAF, Biktarvy)
50/200/25 mg fixed-dose combination

B/F/TAF tablets are packaged in white, high density polyethylene (HDPE) bottles. Each bottle contains 30 tablets, silica gel desiccant and polyester packing material. Each bottle is enclosed with a white, continuous thread, child-resistant polypropylene screw cap with an induction-sealed and aluminum-faced liner.

Study drug(s) to be distributed to centers in the US shall be labeled to meet applicable requirements of the US FDA, EU Guideline to Good Manufacturing Practice - Annex 13 (Investigational Medicinal Products), and/or other local regulations.

5.2.3. Storage and Handling

Study drugs should be stored at controlled room temperature of 25 °C (77 °F); excursions are permitted between 15 °C and 30 °C (59 °F and 86 °F). Storage conditions are specified on the label. Until dispensed to the subjects, all bottles of study drug should be stored in a securely locked area, accessible only to authorized site personnel.

To ensure the stability and proper identification, study drug should not be stored in a container other than the container in which they were supplied.

Consideration should be given to handling, preparation, and disposal through measures that minimize drug contact with the body. Appropriate precautions should be followed to avoid direct eye contact or exposure through inhalation when handling.

5.3. Dosage and Administration of E/C/F/TAF

E/C/F/TAF FDC and B/F/TAF FDC tablets will be provided by Gilead Sciences.

E/C/F/TAF FDC tablets containing 150 mg of EVG, 150 mg of COBI, 200 mg of FTC, and 10 mg of TAF will be provided to all eligible subjects at Day 1. Study drug will be administered orally at approximately the same time each day with food.

B/F/TAF FDC tablets containing 50 mg of bictegravir, 200 mg of emtricitabine, and 25 mg of TAF will be provided to all subjects who participate in the OL rollover extension of B/F/TAF FDC at the End of E/C/F/TAF Visit. Study drug will be administered orally at approximately the same time each day with food.

On the day of hemodialysis, study drug administration should occur after completion of hemodialysis.

Subjects will be instructed to bring all study drug in the original container at each clinic visit for drug accountability (unless otherwise specified in the study procedures sections of this protocol). The Investigator will be responsible for maintaining accurate records for all study drug bottles dispensed and tablets returned. The inventory and dispensing logs must be available for inspection by the study monitor. Study drug supplies, including partially used or empty bottles, must be accounted for by the study monitor prior to destruction or return.

5.4. Prior and Concomitant Medications

- For subjects receiving hormonal contraceptives, investigators and/or the subject's healthcare providers should consider additional methods of contraception, as concentrations of ethinyl estradiol may decrease and progestin level may increase on co-administration with study drug.
- The use of medications for the treatment of HIV, other than study drug, is prohibited.
- For subjects receiving concomitant medications that are highly dependent on CYP3A for clearance and for which elevated plasma concentrations are associated with serious adverse events, investigators and/or the subject's healthcare providers should consider alternative concomitant medications.
- During the study, subjects may not receive any of the following concomitant medications:
 - Competitors of renal excretion (e.g., probenecid; high-dose non-steroidal anti-inflammatory drugs)
 - Known nephrotoxic drugs (e.g., aminoglycosides, amphotericin B, vancomycin, cidofovir, foscarnet, cisplatin and pentamidine)
- Medications listed in the following tables and use of herbal/natural supplements are excluded or should be used with caution while subjects are participating in the study. Any concomitant medication requiring adjustment or discontinuation due to renal impairment or a change in renal function on study should be managed per that drug's prescribing information.

Table 5-1. Prior and Concomitant Medications (E/C/F/TAF)

Drug Class	Agents Disallowed	Use Discouraged and To Be Used With Caution
Acid Reducing Agents Antacids		Concentration of study drug may decrease with antacids. Subjects may not take antacids (eg, Tums, Mylanta); the ulcer medication sucralfate (Carafate); or vitamin or mineral supplements that contain calcium, iron or zinc for a minimum of 2 hours before and 2 hours after any dose of study drug.
Alpha Adrenergic Receptor Antagonists	Alfuzosin	
Analgesics		Tramadol, Propoxyphene: Concentrations may increase with study drug(s); clinical monitoring is recommended.
Antiarrhythmics		Amiodarone, Flecainide, Quinidine, Propafenone, Systemic Lidocaine, Mexiletine, Disopyramide: Concentrations may increase with study drug(s) resulting in a potential for cardiac arrhythmias; clinical and ECG monitoring is recommended.
Calcium Channel Blockers	Bepridil	Felodipine, Nifedipine, Nicardipine, Verapamil, Diltiazem, Amlodipine: Concentrations may increase with study drug(s). Clinical and ECG monitoring of subjects is recommended
Digoxin		Digoxin: Concomitant use may result in increased levels; use with caution and with appropriate monitoring of serum digoxin levels. Digoxin therapy should be initiated at the lower dose, and the dose should be titrated to clinical response.
Direct Oral Anticoagulants (DOACs)	Apixaban, Rivaroxaban	DOACs are primarily metabolized by CYP3A4 and/or transported by P-gp. Coadministration with GENVOYA may result in increased plasma concentrations of the DOAC, which may lead to an increased bleeding risk. Dabigatran, Edoxaban, Betrixaban: Clinical monitoring and/or dose adjustment is recommended when a DOAC transported by P-gp, including dabigatran, edoxaban, or betrixaban is coadministered with GENVOYA. Refer to the prescribing information of the coadministered DOAC.
Antibacterials		Clarithromycin and Telithromycin: Concentrations may be altered with study drug(s); consider an alternative.
Anticoagulants		Warfarin: Concentrations may increase or decrease with study drug(s); appropriate INR (International Normalized Ratio) monitoring is recommended.

Drug Class	Agents Disallowed	Use Discouraged and To Be Used With Caution
Anticonvulsants	Phenobarbital, Phenytoin, Carbamazepine, Oxcarbazepine	Ethosuximide, Divalproex, Lamotrigine: Concentrations may increase with study drug(s); clinical monitoring is recommended.
Antidepressants		Selective serotonin reuptake inhibitors (SSRIs): A dose reduction may be required for most drugs of this class with the exception of sertraline. Tricyclics: Concentrations may increase or decrease with study drug(s). Concentration monitoring is recommended to ensure adequate clinical response. Trazodone: Concomitant use with CYP3A inhibitors results in increased concentrations and adverse events; dose reduction should be considered.
Antifungals		Ketoconazole and Itraconazole: Concomitant use with study drug may result in an increase in concentrations. Daily dose of ketoconazole and itraconazole should be restricted to 200 mg. Subjects receiving ketoconazole or itraconazole should be monitored for adequate clinical response. Voriconazole: Concomitant use with study drug may result in an increase in concentrations. Clinical monitoring may be needed.
Antigout		Colchicine: Concentrations may increase with study drug(s). Dose reductions of colchicine may be required. Should not be coadministered in patients with renal or hepatic impairment. Treatment of Gout Flare: 0.6 mg (1 tablet) × 1 dose, followed by 0.3 mg (half tablet) 1 hour later. Treatment course may be repeated no earlier than 3 days. Prophylaxis of Gout Flares: If the original regimen was 0.6 mg twice a day, the regimen should be adjusted to 0.3 mg once a day. If the original regimen was 0.6 mg once a day, the regimen should be adjusted to 0.3 mg once every other day. Treatment of Familial Mediterranean Fever: Maximum daily dose of 0.6 mg (may be given as 0.3 mg twice a day).
Antihistamines	Astemizole, Terfenadine	
Antimycobacterials	Rifampin, Rifapentine, Rifabutin	
β-Blockers		Metoprolol, Timolol: Clinical and ECG monitoring of subjects is recommended. A dose decrease may be needed.

Drug Class	Agents Disallowed	Use Discouraged and To Be Used With Caution
Corticosteroids (all routes excluding cutaneous): dexamethasone (oral)		
Systemic dexamethasone, a CYP3A inducer, may significantly decrease elvitegravir and cobicistat plasma concentrations, which may result in loss of therapeutic effect and development of resistance. Alternative corticosteroids should be considered.
 
Use of Prednisone as a steroid burst (\leq 1 week of use) should be monitored appropriately.
 
Betamethasone, Budesonide, Fluticasone, Mometasone, Triamcinolone: Coadministration with corticosteroids that are sensitive to CYP3A inhibition can increase the risk for Cushing's syndrome and adrenal suppression, which have been reported during postmarketing use of cobicistat-containing products. Consider the risk of systemic corticosteroid effects if GENVOYA is coadministered with corticosteroids that are sensitive to CYP3A inhibition.
 
Alternative corticosteroids should be considered, particularly for long-term use.

Endothelin receptor antagonists		Bosentan: coadministration may lead to decreased elvitegravir exposures and loss of therapeutic effect and development of resistance. Alternative endothelin receptor antagonists may be considered.
Ergot Derivatives	Ergotamine, Ergonovine Dihydroergotamine Methylergonovine Ergometrine	
GI Motility Agents	Cisapride	
Herbal/Natural Supplements	St. John's Wort, Echinacea	
HMG-CoA Reductase Inhibitors	Simvastatin, Lovastatin	Atorvastatin: Concentrations may increase with study drug(s). Start with the lowest dose; gradual increase in dose may be tailored to clinical response. Careful monitoring for signs and symptoms of muscle weakness or myopathy, including rhabdomyolysis.
Hormonal Contraceptives		Drospirenone: Plasma concentrations of drospirenone may be increased when coadministered with cobicistat-containing products. Clinical monitoring is recommended due to the potential for hyperkalemia.
Immunosuppressants		Cyclosporine, Rapamycin, Sirolimus, Tacrolimus: Concentrations may increase with study drug(s). Therapeutic monitoring should be considered.
Inhaled Beta Agonist	Salmeterol	

Drug Class	Agents Disallowed	Use Discouraged and To Be Used With Caution
Neuroleptics	Pimozide	Perphenazine, Risperidone, Thioridazine: A dose decrease may be needed.
Opiates		Methadone: Methadone exposures are unaffected upon coadministration with elvitegravir and cobicistat. No dose adjustment of methadone is required upon coadministration with study drug(s). Meperidine (Pethidine): Dosage increase and long-term use are not recommended due to increased levels of metabolite normeperidine, which has analgesic and CNS stimulant (eg, seizures) activities. Buprenorphine: Concentrations of buprenorphine and norbuprenorphine are modestly increased and concentrations of naloxone are modestly decreased when coadministered with elvitegravir and cobicistat, with no effect on opioid pharmacodynamics. The concentration changes are not considered clinically relevant and no dose adjustment of buprenorphine/naloxone is required upon coadministration with study drug(s).
Phosphodiesterase-5 Inhibitors	Sildenafil (for PAH)	Pulmonary Arterial Hypertension: Tadalafil: Caution should be exercised, including consideration of dose reduction, when coadministered for treatment of pulmonary arterial hypertension. Erectile Dysfunction: Sildenafil, Vardenafil, Tadalafil: It is recommended that a single dose of Sildenafil no more than 25 mg in 48 hours, Vardenafil no more than 2.5 mg in 72 hours, or Tadalafil no more than 10 mg in 72 hours be coadministered.
Sedatives/Hypnotics	Orally administered Midazolam, Triazolam	Buspirone, Clorazepate, Diazepam, Estazolam, Flurazepam, Zolpidem: A dose decrease may be needed for these drugs. Clinical monitoring is recommended.

Table 5-2. Prior and Concomitant Medications (Open-Label B/F/TAF Rollover Extension)

Drug Class	Agents Disallowed*	Use Discouraged and To Be Used With Caution
Acid Reducing Agents Antacids Buffered medications		Antacids containing Al/Mg or Calcium: B/F/TAF can be taken under fasting conditions 2 hours before antacids containing Al/Mg or calcium. Routine administration of B/F/TAF simultaneously with, or 2 hours after, antacids containing Al/Mg or calcium is not recommended. Supplements containing Calcium or Iron: B/F/TAF and supplements containing calcium or iron can be taken together with food. Routine administration of B/F/TAF under fasting conditions simultaneously with, or 2 hours after, supplements containing calcium or iron are not recommended.
Antiarrhythmic Agent	Dofetilide	
Anticonvulsants	Phenobarbital, Phenytoin, Carbamazepine, Oxcarbazepine	
Antimycobacterials	Rifampin, Rifapentine, Rifabutin	
Antiretrovirals	Any antiretroviral drug that is not part of the study regimen	
GI Motility Agents	Cisapride	
Herbal/Natural Supplements	St. John's Wort, Echinacea	
Oral Hypoglycemic Agent		Refer to the prescribing information of metformin for assessing the benefit and risk of concomitant use of B/F/TAF and metformin.

- Should subjects have a need to initiate treatment with any disallowed concomitant medication, the Gilead Sciences Medical Monitor must be consulted prior to initiation of the new medication. In instances where an excluded medication is initiated prior to discussion with the Sponsor, the Investigator must notify Gilead Sciences as soon as he/she is aware of the use of the disallowed medication.

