4.2. Inclusion Criteria

Subjects must meet **all** of the following inclusion criteria to be eligible for participation in this study.

- 1) The ability to understand and sign a written informed consent form, which must be obtained prior to initiation of screening procedures
- 2) Age \geq 18 years
- 3) Currently receiving a stable antiretroviral regimen for \geq 6 consecutive months prior to screening
- 4) Documented plasma HIV-1 RNA concentrations $<$ 50 copies/mL for at least 6 months preceding the screening visit (measured at least twice using the same assay) and have HIV-1 RNA $<$ 50 copies/mL at screening
 - a) In the preceding 6 months prior to screening, one episode of “blip” (HIV-1 RNA \geq 50 copies/mL and $<$ 400 copies/mL) is acceptable, only if HIV-1 RNA is $<$ 50 copies/mL immediately before and after the blip.
 - b) To determine virologic suppression in the preceding 6 months prior to screening, the lower limit of quantification (LLOQ) by the local HIV-1 RNA assay may be used, only if its LLOQ is greater than 50 copies/mL (e.g. LLOQ of 75 copies/mL)
- 5) No documented history of HIV-1 resistance to EVG, FTC, 3TC or TFV and no history of switching off EVG, FTC, 3TC or TFV due to concern for resistance
- 6) CD4+ T cell count of \geq 200 cells/ μ L
- 7) ESRD with eGFR $<$ 15 mL/min by Cockcroft-Gault formula for creatinine clearance
{Cockcroft 1976}
$$\text{Male: } \frac{(140 - \text{age in years}) \times (\text{wt in kg})}{72 \times (\text{serum creatinine in mg/dL})} = \text{Cl}_{\text{cr}} \text{ (mL/min)}$$
$$\text{Female: } \frac{(140 - \text{age in years}) \times (\text{wt in kg})}{72 \times (\text{serum creatinine in mg/dL})} \times 0.85 = \text{Cl}_{\text{cr}} \text{ (mL/min)}$$
- 8) On chronic HD for \geq 6 months prior to screening

- 9) Hepatic transaminases (AST and ALT) $\leq 5 \times$ upper limit of normal (ULN)
- 10) Chronic Hepatitis C (HCV) infection allowed if liver function is stable for ≥ 6 months prior to screening: ALT $\leq 10 \times$ ULN, AST $\leq 10 \times$ ULN, total bilirubin ≤ 2.5 , or normal direct bilirubin (subjects with documented Gilbert's Syndrome or hyperbilirubinemia due to atazanavir therapy may have total bilirubin up to $5 \times$ ULN), INR ≤ 1.5 and albumin ≥ 3 g/dL; no evidence of cirrhosis or hepatocellular carcinoma by imaging in the last 12 months
- 11) Adequate hematologic function (absolute neutrophil count $\geq 1,000/\text{mm}^3$; platelets $\geq 50,000/\text{mm}^3$; hemoglobin ≥ 8.5 g/dL)

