4.3. Exclusion Criteria

Subjects who meet any of the following exclusion criteria are not to be enrolled in this study.

- 1) Hepatitis B surface antigen (HBsAg) positive
- 2) Subjects experiencing decompensated cirrhosis (e.g., ascites, encephalopathy, etc.)
- 3) Treatment with an HIV-1 immunotherapeutic vaccine within 90 days of screening
- 4) Treatment with radiation, cytotoxic chemotherapeutic agents, or any immunomodulator within 30 days of screening
- 5) Any other clinical history, condition, or test result that, in the opinion of the Investigator, would make the subject unsuitable for the study or unable to comply with dosing requirements
- 6) Administration of other investigational agents (unless approved by Gilead Sciences). Participation in any other clinical trial, including observational trials, without prior approval from the sponsor is prohibited while participating in this trial.
- 7) History or presence of allergy or intolerance to the study drugs or their components
- 8) A new AIDS-defining condition (excluding CD4+ T cell count and percentage criteria) diagnosed within the 30 days prior to screening, with the exception of oropharyngeal candidiasis (see [Appendix 8](#))
- 9) Have an implanted defibrillator or pacemaker
- 10) Current alcohol or substance use judged by the Investigator to potentially interfere with subject study compliance
- 11) A history of malignancy within the past 5 years (prior to screening) or ongoing malignancy other than cutaneous Kaposi's sarcoma (KS), basal cell carcinoma, or resected, non-invasive carcinoma
- 12) Received solid organ or bone marrow transplant
- 13) Significant bone disease (e.g., osteomalacia, chronic osteomyelitis, osteogenesis imperfecta, osteochondroses), or multiple bone fractures
- 14) Active, serious infections (other than HIV-1 infection) requiring parenteral antibiotic or antifungal therapy within 30 days prior to Day 1
- 15) Systemic chemotherapeutic agents, systemic corticosteroids (except short-term use of prednisone as a steroid burst [≤ 1 week of use]), immunosuppressant, or immunomodulating agents
- 16) Subjects receiving ongoing therapy with any of the following medications in the [Table 4-1](#) below, including drugs not to be used with EVG, COBI, FTC, TAF, and BIC

Table 4-1. Disallowed Agents (E/C/F/TAF Phase)

Drug Class	Agents Disallowed ^a
Alpha Adrenergic Receptor Antagonists	Alfuzosin
Calcium Channel Blockers	Bepridil

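### Table 5-1 prints three colchicine regimens that no subject in this all-ESRD trial can use, and does not list the drug as disallowed

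*Protocol*

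**What the plan says.** Protocol Section 5.4 introduces its medication tables by saying that the listed drugs "are excluded or should be used with caution while subjects are participating in the study". In Table 5-1, for the E/C/F/TAF phase, the Antigout row contains colchicine alone. Its disallowed field is blank and all of its text is in the caution column. In order, that cell:

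- says concentrations may rise with study drug;
- says "Dose reductions of colchicine may be required";
- says the drug "Should not be coadministered in patients with renal or hepatic impairment";
- gives doses for treating a gout flare, for gout prophylaxis (for example, "the regimen should be adjusted to 0.3 mg once a day" when the previous dose was 0.6 mg twice daily) and for familial Mediterranean fever.

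Inclusion criterion 7 (Section 4.2) requires ESRD with eGFR below "15 mL/min by Cockcroft-Gault formula for creatinine clearance", and criterion 8 requires at least 6 months of chronic hemodialysis. Table 4-1, the disallowed list attached to exclusion criterion 16, does not name colchicine.

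The last bullet of Section 5.4 requires consultation with the Medical Monitor before a disallowed drug is started, and notification of the sponsor if an excluded drug was started without discussion.

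**The concern.** The cell gives a correct warning for this population and follows it with doses that the warning rules out for everyone enrolled. A site managing a gout flare would look in the Antigout row and find an explicit regimen, in a column that signals permitted use with care. Section 5.4 also bars probenecid and high-dose non-steroidal anti-inflammatory drugs during the study, which makes a ready-made colchicine regimen more likely to be noticed. A short prednisone burst is contemplated elsewhere in the table, so colchicine is not the only option.

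At stake is subject safety through clear instructions: whether a site would treat the drug as barred, and whether it would know to call the Medical Monitor first. The sample size and the planned analyses are not involved.

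**Working it through.** No arithmetic beyond counting applies, and the plan states no figure on this point. The check sets the relevant texts against each other.

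1. **Who is covered by the warning?** Criteria 7 and 8 together make every eligible subject a hemodialysis patient with eGFR below 15 mL/min. The warning concerns renal impairment, so it covers the whole population.

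2. **How many printed regimens remain usable?** Three indications carry doses. The warning is not limited by indication, so it removes all three: 3 − 3 = 0 usable. Counting the two prophylaxis adjustments separately gives 4 − 4 = 0.

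3. **Is colchicine on a disallowed list for this phase?** There are two: Table 4-1 and the disallowed column of Table 5-1. Colchicine is on 0 of 2. Table 5-2 (B/F/TAF extension) has no colchicine entry, so the conflicting text is confined to the E/C/F/TAF phase.

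4. **Does the same table separate barred from permitted use elsewhere?** Yes. Sildenafil for pulmonary arterial hypertension is in the disallowed column, and sildenafil doses appear in the caution column only for erectile dysfunction. Colchicine has no permitted use here, yet it has doses and no disallowed entry.

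5. **Do the other provisions settle it?**

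| Provision | What it covers | Does it reach colchicine? |
|---|---|---|
| Medical Monitor bullet, 5.4 | Disallowed or excluded drugs | Not clearly: the introduction to the tables distinguishes excluded drugs from caution drugs, and colchicine is in the caution column |
| Exclusion criterion 16 | Table 4-1 agents, "including drugs not to be used with EVG, COBI, FTC, TAF, and BIC" | Not on its natural reading, since the phrase qualifies a table that omits colchicine |
| Prescribing-information sentence, 5.4 | "Any concomitant medication requiring adjustment or discontinuation due to renal impairment" | Yes in substance, but it names no drug, sits outside the table and does not require sponsor contact |
| CYP3A bullet, 5.4 | Drugs highly dependent on CYP3A whose raised levels cause serious events; investigators "should consider alternative concomitant medications" | Possibly, but it is advisory, and the documents do not say that colchicine is in this class |

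6. **How far could an edit reach?** The SAP's disposition shell (Appendix Table 1) shows enrolment complete at 55. SAP Section 2.4 reports the Week 96 analysis as done. Protocol Section 3.2 continues E/C/F/TAF after Week 96 only for US subjects heading for the extension. The SAP was signed in December 2019, its last named E/C/F/TAF visit window is Week 120, and SAP Section 9 describes the pre-dose extension samples as already collected. Neither document gives the number still on E/C/F/TAF. The evidence suggests few or none.

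**The case against.** The strongest reply is that the cell is not contradictory. A prohibition for renally impaired patients, followed by doses, can be read as doses for everyone else. In an all-ESRD trial they are then surplus text, and a site would have to ignore the sentence immediately before the regimens to use them. This stands as logic: the warning, if followed, already bars use. It does not explain why doses for patients who cannot be enrolled should be in the protocol.

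Second, Section 5.4 does not confine binding rules to the disallowed column. It bans renal-excretion competitors and nephrotoxic drugs in running text, and the caution column itself forbids antacids within two hours of a dose and caps ketoconazole and itraconazole at 200 mg daily. A reader could therefore treat colchicine as disallowed in this population and call the Medical Monitor. That is a fair reading, which is why the rule is described here as not clearly reaching the drug. It would be too strong to say that the rule plainly fails to apply, or that the protocol authorizes colchicine.

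Third, the sildenafil comparison is imperfect, because that restriction is by indication and colchicine's is by patient condition. It shows only that the layout can mark a barred use.

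Fourth, the prescribing-information sentence addresses drugs limited by renal impairment. It is a genuine safeguard, although the documents do not reproduce colchicine's prescribing information.

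**Conclusion.** The point holds as a low-priority safety and clarity correction. All three printed regimens are unusable in this trial under the cell's own warning, the drug is on neither disallowed list for the E/C/F/TAF phase, and the requirement to consult the Medical Monitor is ambiguous. This rests on reading the warning as applying to all three indications, which is its plain sense.

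A reader might infer that subjects were given colchicine under these instructions, that some were harmed, or that the Grade 3 or higher adverse event endpoint was affected. The documents support none of these. They report no colchicine user and no related event, and the number of users may be zero. They give no basis for estimating a likelihood of use or harm, so no exposure percentage is offered.

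**What to change.** In Table 5-1, delete the sentence "Dose reductions of colchicine may be required" and the three regimens, and enter colchicine in the disallowed column so that Medical Monitor consultation clearly applies. Add it to Table 4-1 for consistency; with enrolment complete, that entry reaches no new subject. Notify any site with a subject still on E/C/F/TAF. If none remain, the value of the edit lies in preventing reuse of the cell in a later protocol.

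The cost is an edit to two tables and, if needed, one site communication. Any current user on E/C/F/TAF would need an alternative, planned with the Medical Monitor. No legitimate use is lost, because the protocol's own sentence already rules the drug out here.

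No new analysis is needed. SAP Section 8.6.2 already summarizes concomitant non-antiretroviral drugs by preferred name from Study Day 1 to the last E/C/F/TAF dose, so any colchicine use will be visible there.
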